Baseline blood samples (12 mL), saliva (1-2 mL) and urine will be collected and analyzed for buprenorphine and metabolites. We will perform a urine drug screen by immunoassay for drugs of abuse. Blood will also be utilized for determination of catecholamines (epinephrine and nor epinephrine), cotinine, and PBMC analysis. Screening blood chemistries and hematology labs

(AST/SGOT, ALT/SGPT, creatinine, BUN, total protein, albumin, hemoglobin, and platelets) are collected at the first Screening Visit only to establish eligibility. A hematocrit is also required at the first screening visit, unless a result is available from the subject's medical record within the past 4 weeks. If the hematocrit is within normal limits at the first screening visit, it will not be repeated during the remainder of the study. Baseline physiologic measurements (pupillometry, galvanic skin response, blood pressure, and heart rate) will be taken and the subject will subsequently take her medication as prescribed.

Additional blood and saliva samples will be collected at the following time intervals. The maximum amount of blood drawn from a subject on a study day is 103 mL.

Sample/Measurement Type	Dosing	Time Interval
blood & saliva	BID	Baseline and 10, 20, 30, 60, 90, 120, 180, 240, 360, 480, 600, 720 minutes post dose
blood & saliva	TID	Baseline and 10, 20, 30, 60, 90, 120, 180, 240, 300, 360, 420, 480 minutes post dose
blood & saliva	QID	Baseline and 10, 20, 30, 60, 90, 120, 180, 240, 300, 360 minutes post dose
blood & saliva	5 times/day	Baseline and 10, 20, 30, 60, 90, 120, 150, 180, 240, and 300 minutes post dose

Refer to section D.5.xi for blood and saliva collection and processing instructions.

All urine voided from 0-12 hrs. (subject will be asked to empty bladder at 12 hrs for BID dosing, at 8 hours for TID dosing, at 6 hours for QID dosing, and at 5 hours for five times daily dosing) will be collected, total volume recorded and aliquots will be frozen immediately.

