Patients will be at steady state when the pharmacokinetic studies are performed. This will be documented by comparing the concentration at time 0 and at 12 hrs. (less than 20% variation). Plasma concentration-time profiles will be analyzed using both non-compartmental and population pharmacokinetic modeling and simulation approaches. Data will be analyzed using WINNONLIN and NONMEM software. We will compare various pharmacokinetic parameters between pregnant and non-pregnant (postpartum) subjects using a paired t-test as described previously. This will include all non-compartmental data (C_{max}, T_{max}, AUC(0-t), AUC(0-∞), k_e, λ_Z, CL/F, CLR, V_d/F, V_{ss}, AUMC, and MRT). Population pharmacokinetic model will be developed using nonlinear mixed effects modeling software (NONMEM version 7.1; ICON Development Solutions, [name]), GNU Fortran 95 compiler and PLT tools (version 5.1.0). The general linear model under steady state will be constructed using ADVAN5 SS5 subroutines. In order to identify the covariates that influence the pharmacokinetics of BUP, the following covariates will be evaluated: maternal age (years), body weight (kg), race, gestational age, serum albumin, serum creatinine (mg/dL), salivary PH, buprenorphine dose, tablet size and co-medications and SNPs of the various metabolizing enzymes. For covariate selection, univariate analysis with stepwise forward addition ($p < 0.01$) and backward elimination ($p < 0.001$) procedures will be followed. The covariates that significantly influence the pharmacokinetics of BUP and its metabolite will be incorporated in the final model. The predictive performance of the model will be internally evaluated using prediction corrected-visual predictive check, where 1500 data sets will be simulated using the parameter estimates in the final model. The 50th percentile concentration (median) and the 5th and 95th percentile concentrations (90% prediction interval) will be plotted and compared to the observed concentrations. The data obtained will be used to validate the predictions of SIMCYP-PBPK simulation from the basic/translation project.

D.6. Preliminary Data Relevant to the Primary Outcome

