We have developed a HPLC-MS-MS assay for BUP and metabolites with a lower limit of quantitation of the assay for BUP (BUP), of 0.05 ng/ml, while that for nor-BUP is 0.5 ng/ml. We have performed an intensive PK study on 12 subjects. The dose-adjusted AUC in the third trimester of pregnancy (2.4 ng/ml).hr was lower than in the postpartum period (4.0 ng/ml).hr while clearance is higher in pregnancy (589 L/hr) than in the postpartum period (288 L/hr). There was a large variation (cv = 50%) in both AUC and clearance values. None of the subjects in this cohort was studied in the first half of pregnancy.

D.7. Potential Problems, Alternative Strategies, Benchmarks

Recruitment is a potential problem in any clinical trial and if other sites in the OPPTB do not have access to patients on BUP in their own institutions they may have difficulty recruiting subjects. These patients have difficulty with compliance to drug treatment regimens so dropout may be higher than in most clinical trials. Postpartum studies are difficult because of childcare issues and this may hamper recruitment. These challenges can be overcome by identifying physicians and clinics that write prescriptions for BUP and care for such patients. The childcare issue can be addressed by financial incentives or by allowing the mother to bring her baby to the CRC during study days.

D.8. Feasibility

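### The 0-versus-12-hour steady-state check has samples only for BID women, and paired tests of AUC(0-∞) and terminal-slope parameters are unreliable from 5 to 12 h steady-state profiles

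*Combined protocol and SAP*

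**What the plan says.** Section D.5.xiii (Secondary Hypotheses) states that women will be at steady state when studied and gives one rule for showing it: "This will be documented by comparing the concentration at time 0 and at 12 hrs. (less than 20% variation". It gives no version for other schedules and no consequence if the check fails.

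Section D.4.i admits women dosing two, three, four or five times daily. In section D.5.vi the last blood sample is at 720 min for BID, 480 for TID, 360 for QID and 300 for five times daily. The QID row reads "Baseline and 10, 20, 30, 60, 90, 120, 180, 240, 300, 360 minutes post dose". For urine, the same section names 12 h and then adapts it: "All urine voided from 0-12 hrs. (subject will be asked to empty bladder at 12 hrs for BID dosing", followed by "at 8 hours for TID dosing, at 6 hours for QID dosing, and at 5 hours for five times daily dosing".

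Section D.5.xiii then plans paired pregnancy-versus-postpartum t-tests of all noncompartmental results. The list includes "AUC(0-t), AUC(0-∞), k_e, λ_Z, CL/F, CLR", and also V_d/F, Vss, AUMC and MRT. AUC over the dosing interval is not named, the formula for CL/F is not given, and no limit is set on the extrapolated share or the quality of the terminal fit. The population model also assumes steady state: "The general linear model under steady state will be constructed using ADVAN5 SS5 subroutines".

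Section A gives a non-pregnant plasma half-life of about 22 h. Section D.6 reports that "clearance is higher in pregnancy (589 L/hr) than in the postpartum period (288 L/hr", and "The dose-adjusted AUC in the third trimester of pregnancy (2.4 ng/ml).hr was lower than in the postpartum period (4.0 ng/ml).hr".

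**The concern.** There are two separate problems.

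First, as written, the only concentration check of steady state cannot be carried out for three of the four eligible schedules. The SS5 population model relies on steady state, and so does any clearance computed as dose over one-interval AUC.

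Second, AUC(0-∞) equals per-dose exposure after a single dose. At steady state the measured curve already contains drug from earlier doses, so extrapolating it to infinity overstates per-dose exposure by a factor that depends on half-life and dosing interval. If either differs between the pregnancy and postpartum visits, the paired comparison is distorted. Schedules can differ: the 7-day stability rule in D.5.iv applies to each visit separately, and D.5.iii leaves clinical management alone. Independently of steady state, a 5 to 12 h window is too short to estimate a terminal slope near 22 h, which affects k_e, λ_Z, V_d/F, Vss and MRT.

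At stake is a secondary table whose AUC(0-∞) ratios could disagree with the AUC(0-t) ratios and mislead readers about exposure in pregnancy.

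**Working it through.** **Sampling against the rule.** The D.5.vi lists contain 12, 12, 10 and 10 post-dose times, matching the counts in the D.1 table, with visits of 13, 9, 7 and 6 h. A 12 h sample therefore exists for one schedule of four.

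**Is steady state plausible?** 7 days = 168 h, and 168/22 = 7.6 half-lives, so 1 − 2^(−7.6) = 99.5% is attained. Yes, if doses are taken.

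**AUC(0-∞) at steady state, one compartment.** With last sample t, interval tau and half-life h:
- extrapolated share = exp(−ln2·t/h)
- R = AUC(0-∞)/AUC(0-tau) = 1/(1 − exp(−ln2·tau/h))

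**Two compartments (assumed shapes, no assay noise).** Twelve steady-state profiles with evenly spaced doses: terminal half-life 22 h; distribution half-life 1.5 or 3 h; 20, 50 or 80% of AUC in the terminal phase; ka 1 or 3 per h. D.5.vi sampling times, linear trapezoid, slope from the last three samples.

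| Schedule | Window/22 h | Extrapolated share, 1-cpt | R, 1-cpt | R, 2-cpt | Fitted half-life, 2-cpt (truth 22 h) |
|---|---|---|---|---|---|
| BID, 12 h | 0.55 | 69% | 3.18 | 1.11–2.39 | 4.1–17.3 h |
| TID, 8 h | 0.36 | 78% | 4.49 | 1.15–2.81 | 2.7–13.4 h |
| QID, 6 h | 0.27 | 83% | 5.81 | 1.21–3.41 | 2.3–11.5 h |
| Five times daily, 5 h | 0.23 | 85% | 6.86 | 1.29–4.21 | 2.2–11.8 h |

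The one-compartment R for five times daily uses 5 h; with 24/5 = 4.8 h it is 7.1.

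Assay noise adds to the slope problem. With one compartment, 22 h, an assumed 10% residual CV and the last four points, the fitted slope was non-positive in 8, 24, 24 and 28% of simulated profiles. For BID the 5th to 95th percentile of fitted half-life was 10 to 124 h.

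**Effect on the pregnancy/postpartum ratio.** Apparent ratio = true ratio × R(pregnancy)/R(postpartum). The D.6 clearances give a true ratio of 288/589 = 0.49; the D.6 AUCs give 2.4/4.0 = 0.60. With volume constant, the one-compartment half-life in pregnancy is 22 × 288/589 = 10.8 h or 22 × 0.60 = 13.2 h. Example for BID: R is 1.86 at 10.8 h, so 0.489 × 1.86/3.18 = 0.286.

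| Case | True | AUC(0-∞), 1-cpt | AUC(0-∞), 2-cpt | AUC(0-t), 2-cpt |
|---|---|---|---|---|
| D.6 clearances, volume constant | 0.49 | 0.26–0.29 | 0.28–0.48 | 0.48–0.49 |
| D.6 AUCs, volume constant | 0.60 | 0.38–0.40 | 0.40–0.59 | 0.60 |
| QID in pregnancy, BID postpartum, same PK | 1.00 | 5.81/3.18 = 1.83 | 1.05–1.55 | 0.99–1.00 |
| Half-life longer in pregnancy (30 h assumed) | 0.49 | 0.64–0.65 | not run | not run |

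The distortion can go either way. If half-life and schedule are unchanged, the two R values cancel.

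**What an end-of-interval check can show.** Let x = exp(−ln2·tau/22). If the dose before the visit was skipped, the end-of-interval/time-0 ratio in one compartment is x + (1 − x)/x: 1.14, 1.06, 1.04 and 1.02 by schedule, all inside 20%. With two compartments it is about 1.1 to 2.45. Conversely, at true steady state an overnight gap 2 h longer than the interval gives ratios of up to 1.32 for BID, 1.63 for TID and 1.76 for QID (two-compartment cases, including raised clearance). The check can therefore pass a skipped dose and fail a compliant woman.

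**Limits of AUC(0-tau).** With an overnight gap 3 h longer, the morning AUC(0-tau) is 0.87–0.95 of dose/CL for QID. For five times daily the lowest value is 0.86 if integrated to the 5 h sample and 0.84 if cut at 4.8 h.

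**The case against.** Much of the first part is leftover wording. Visit length, blood sampling and urine collection were all adapted by schedule, and the urine text itself opens with 12 h before listing 12, 8, 6 and 5 h. Every schedule already has an end-of-interval sample, and the number of non-BID women is not stated. This stands: a one-line clarification resolves the contradiction.

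The check is also weak evidence, as shown above. The PK dose is the morning dose (D.5.v), so an overnight gap longer than the dosing interval is plausible for TID, QID and five times daily. This stands too, and is why the check should not become an exclusion rule.

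On the second part, the tests are secondary, AUC(0-t) is already listed, population modelling is planned, and no decision hangs on AUC(0-∞) or λ_Z. The size is strongly model-dependent: at the mild end 0.49 reads 0.48. All of this limits the importance. It does not rescue the tests, because the plan has no means of telling which case applies and a 5 to 12 h window cannot supply one.

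A reader might infer that the women are not at steady state, or that the primary result is biased. The documents support neither. Seven days on a stable dose is ample at 22 h. The primary measure is dose-adjusted AUC, sampling spans about one interval on every schedule, and AUC(0-t) stayed within about 1% of the true ratio in the evenly spaced cases.

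**Conclusion.** Both parts hold within limits. The 0-versus-12 h rule and the D.5.vi sampling table conflict for three of four schedules and must be reconciled; what is missing is documentation of steady state, not steady state itself.

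The planned paired tests of AUC(0-∞) and terminal-slope parameters are unreliable. AUC(0-∞) exceeds AUC(0-tau) by a factor of 1.1 to 6.9. A true ratio of 0.49 could read 0.26 to 0.48 if volume is constant, and a QID-to-BID switch with no PK change could read 1.05 to 1.83. The terminal-slope failure comes from the short window, and its direction is firm. The size of the AUC(0-∞) error is not: it rests on the 22 h half-life, constant volume and assumed profile shapes, and it vanishes if half-life and schedule are the same at both visits. It would be wrong to quote the three- to sevenfold factor as established.

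Importance lies between minor and should-fix: the affected analyses are secondary, the share of non-BID women is not stated, and the primary comparison is not shown to be biased.

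**What to change.** (a) Define the check as time 0 against the end-of-interval sample of the woman's own schedule (720, 480, 360 or 300 min). Record the clock times of the preceding doses. Report the check descriptively as supporting evidence, noting that an uneven overnight gap can fail it at true steady state and that it can miss a skipped dose. Do not exclude visits on it.

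(b) In the secondary comparisons use dose-adjusted AUC over the dosing interval, with CL/F = dose/AUC(0-tau). State that it is approximate when gaps are uneven: about 5 to 14% low for QID or five times daily with a 3 h longer overnight gap in the two-compartment cases, and up to 16% if the five-times-daily AUC is cut at 4.8 h. For CLR, use the AUC over the same window as the urine collection, which is 0–5 h for five times daily.

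(c) Do not run paired tests on AUC(0-∞), k_e, λ_Z, V_d/F, Vss or MRT, or on AUMC if extrapolated. Report them descriptively at most. Take any half-life or volume from the planned population model with its precision, and say that the short window limits it.

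Cost: wording, the loss of a few secondary tests, and one added data item. Section D.5.ii already records last-dose time with the screening sample. No new blood is needed.

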Substance abuse costs our nation over \$600 billion annually. Drug addiction treatment reduces drug use and has been shown to reduce the health and societal cost far more than the actual cost of the treatment. Treatment is also much less expensive than other options. Outcomes of drug treatment programs are dependent on adequate treatment length and drop out is one of the major problems in the current treatment program. It is therefore critical to optimize drug dosing regimens in patients to improve adherence and success of the treatment programs. In 2012, an estimated 400,000 adults aged 18 or older were current illicit drug users. Many of these were pregnant women. In the most recent National Survey on Drug Use and Health (2012), 6% of pregnant women reported using illicit substances within the past 30 days¹. Azadi et al found that 3% of women were urine-positive for illicit opioids at the time of delivery². Currently, the standard of care for an opioid-dependent pregnant woman in most institutions is methadone, however buprenorphine (BUP) is also used for this indication as it is FDA-approved for opioid addiction although not specifically for pregnant women. There has been increasing evidence that BUP may have comparable efficacy to methadone, and may have fewer severe neonatal complications especially neonatal abstinence syndrome (NAS). In a recent study, BUP-exposed, as opposed to methadone exposed, neonates required significantly less morphine for treatment of NAS, had significantly shorter duration of treatment for NAS and had significantly shorter hospital stays³. Methadone, a full μ agonist, has significant adverse reactions such as Q-T prolongation, potential for life-threatening respiratory depression and extreme sedation⁴⁻⁶. Conversion from illicit narcotic use to methadone commonly requires hospitalization for 3-4 days as the dose of methadone is titrated upward based on the patient's symptomatology^{4,5}. Upon hospital discharge methadone treated patients receive daily dosing of medication at outpatient clinics that monitor the patients for continued illicit drug use. This requirement is extremely burdensome on the patients since many do not have transportation and they must arrive at the clinics in the morning. BUP, a partial μ agonist, has decreased severity of adverse reactions and therefore physicians are able to convert patients on an outpatient basis. The patient is given a 1-4 week supply of oral medication thus eliminating the burdensome task of attending daily clinics for drug administration. These benefits of BUP are changing the management of drug addiction dramatically and more institutions will turn from in-patient treatment with methadone to the outpatient strategy with BUP. The American College of Obstetricians and Gynecologists in its 2012 Committee Opinion indicates that the literature "supports the use of buprenorphine as first line treatment for pregnant opioid –dependent women"⁷. Similarly the American Society of Addiction Medicine supports the use of buprenorphine in opioid- addicted pregnant women⁸ and the World Health Organization (WHO) which encourages availability of a buprenorphine option has described the worldwide availability of buprenorphine⁹. The dosing of BUP currently is based on studies in men and non-pregnant women and limited animal data that related plasma concentrations of BUP to the degree of saturation of the μ receptor in the brain¹⁰⁻¹³. These studies suggest that a dose of 16 mg daily saturates 95% of the μ receptors. The plasma half-life in non-pregnant subjects is approximately 22 hours and therefore a dose of 16 mg/day appears to be sufficient to saturate the receptors. The standard recommended dosing regimen for sublingual BUP is therefore 8 mg bid or 16 mg QD. Unlike for methadone, where increased dosing is recommended during pregnancy, currently there are no guidelines on dosing BUP in pregnant women. The dosing regimen used in non-pregnant subjects does not appear to be adequate for pregnant women. Dosing is adjusted to the patient's symptomatology using the Clinical Opiate Withdrawal (COW) score, some of which is subjective and some based on objective physiological parameters. The failure rate for BUP is highest (33%) during the induction period i.e. the time from stopping illicit drug use to the point of achieving a stable dose of BUP³. This suggests that the current treatment regimens for BUP are inadequate for many women. Indeed at Magee-Womens Hospital, using COW scores to determine a dosing regimen has resulted in many women requiring doses higher than the 16 mg daily dose used in non-pregnant subjects. The high failure rate of BUP during induction and the experience at Magee are

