
B. Innovation

Our proposed project challenges the current clinical practice paradigm that defines a dose of BUP for pregnant women that is based on pharmacokinetics in men and non- pregnant women and relies on the COW score to titrate the dose. We will define the pharmacokinetics and pharmacodynamics of BUP in early and late pregnancy and the postpartum period and determine what contributes to the variation in plasma concentrations and response. We will also relate plasma concentrations of BUP and its major metabolites to physiologic parameters that can be used to gauge the amount of drug in mother’s plasma. Our expectation is that we will demonstrate that higher doses of BUP are needed throughout pregnancy and that the dosing regimen can be adjusted using patient covariates and biophysical measurements in addition to the COW scores. Our exploration of pupillometry and the galvanic skin response to gauge maternal BUP satiety in pregnancy is unique and challenges contemporary practice¹⁵⁻¹⁷. There is a strong relationship between plasma BUP concentrations and the saturation of brain μ receptors¹². If μ receptor occupancy is a major determinant of maternal satiety and drug-seeking behavior, then plasma concentrations of BUP and its metabolites are key in achieving these outcomes. Any variation in dosage requirements cannot be attributed to differences in blood brain barrier permeability but may rather reflect differences in absorption or metabolism or elimination of BUP or its metabolites. Therefore, to optimize therapy a direct or indirect measure of plasma BUP is needed.

Measurement of BUP concentrations in plasma requires high sensitivity equipment and therefore not likely to be useful in clinical practice. An indirect non-invasive measure of BUP plasma concentrations is appealing due to convenience, low cost and rapidly available results. COW scores are now the standard by which buprenorphine is dosed but they are flawed as half the parameters are subjective and can be manipulated by the patient. A purely physiological endpoint is less likely to be controlled by the patient. We will evaluate several maternal and newborn variables that might be predictive of NAS. Our approach is unique in that we will have full pharmacokinetic characterization of the mother as well as hair samples and placental P-gp status to enable a much more complete assessment of predictive factors in combination that have previously been reported singly.

C. Specific Aims

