No attempt will be made to mandate clinical management of the subjects. If complications arise, the patient will still be eligible for additional PK studies unless the complication affects the pharmacology of BUP i.e. significant liver or renal disease.

If a patient who consented to any part of this study (Parts A-E) is dismissed from her Medication Assisted Treatment (MAT) clinic due to non-compliance, she will be dismissed from the study and another subject will be recruited to replace her.

If non-prescribed opiates/opioids are detected during any PK screening visits, the subject will be ineligible to complete the pending PK visit. Subjects may be re-screened at a later date as long as they are within the gestational window for the PK visit. If a subject in the PK study has two positive drug screens for non-prescribed opiates/opioids during any screening visits, she will be dismissed from the study and replaced with another study subject.

At the time of enrollment, patients will consent to those components of the study that they wish to participate in. Subjects are required to complete at least one PK study in order to participate in this portion of the study. If a subject consents to portion of the study and they are unable to complete it within the acceptable timeline, they will still be eligible to participate in the remaining

parts of the study they consented to.

D.5.iv. Study PK Visits:

Once the subject has signed the consent form, completed the Screening Visit, and is deemed eligible for the study, the research staff will establish a schedule for the subject to undergo their first PK study. Subjects participating in the PK study must complete at least one PK study.

Screening Visits will be conducted within 1-2 weeks prior to each PK study and subjects must continue to meet the criteria listed in section D.4, with the exception of exclusion criteria items 6 and 7. A urine drug screen (Immunoassay) will be performed on the day of the PK study.

Each PK study, both during and after pregnancy, will be performed after the subject has been on a consistent two, three, four, or five time daily dose of BUP for a minimum of 7 days.

D.5.v. BUP Administration During PK Visit:

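### Symptom-titrated buprenorphine dose is tested as an ordinary stepwise covariate for buprenorphine PK, so a selected dose term may reflect clearance driving dose and can distort the secondary population PK model

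*Combined protocol and SAP*

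**What the plan says.** D.5.xiii, Secondary Hypotheses, sets out a NONMEM population model with a linear structure: "The general linear model under steady state will be constructed using ADVAN5 SS5 subroutines". The covariate candidates start with "maternal age (years), body weight (kg), race, gestational age, serum albumin" and go on to include "salivary PH, buprenorphine dose, tablet size and co-medications and SNPs of the various metabolizing enzymes". For selection, "stepwise forward addition ($p < 0.01$) and backward elimination ($p < 0.001$) procedures will be followed". The plan then states: "The covariates that significantly influence the pharmacokinetics of BUP and its metabolite will be incorporated in the final model".

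Three other places say how dose arises.

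- Section A: "Dosing is adjusted to the patient's symptomatology using the Clinical Opiate Withdrawal (COW) score".
- D.5.iii: "No attempt will be made to mandate clinical management of the subjects". D.5.v adds that each woman brings medication supplied by her own provider or clinic.
- Section B argues that variation in dosage requirements "may rather reflect differences in absorption or metabolism or elimination of BUP or its metabolites".

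The plan does not define dose (daily or per administration) or name the PK parameter on which it is tested. It does not force a pregnancy term into the model, and it has no comparison model without dose.

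**The concern.** The search is meant to find what influences buprenorphine PK. For dose, the null hypothesis is that PK is linear, so clearance does not depend on dose. The stepwise test is valid for that null only if dose is unrelated to a woman's own clearance. Under symptom titration, a woman who clears the drug faster may end on a higher dose. Dose and clearance are then correlated even though PK is linear, because clearance drove the dose. A strict backward threshold limits chance findings but does nothing about this confounding.

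At stake is what the final population model can be used for. A false dose term would be read as non-linear PK and would understate the exposure reached when dose rises. It would also absorb part of the genotype effects in Aim 2 and, in some circumstances, part of the pregnancy effect.

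**Working it through.** **Plan's own figure.** The plan computes nothing for the covariate search. Its only calculated figure is the 37 women for the primary question. A two-sample formula with δ = 0.5 × 2.34 = 1.17 and SD 1.82 gives 2(1.960 + 0.842)² × 1.82² / 1.17² = 37.98, so 38. That is close to 37, and this point does not depend on it.

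**Inputs from the documents.** 40 women (D.1); CV 50% for clearance, and clearance 589 L/hr in pregnancy against 288 L/hr postpartum, ratio 2.05 (D.6); 2 mg and 8 mg tablets (D.5.v); thresholds 0.01 and 0.001, which are likelihood drops of 6.635 and 10.828 (D.5.xiii).

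**Assumptions not in the documents.** Log daily dose = constant + g × log CL + noise with log-SD s, rounded to 2 mg steps and limited to 4–32 mg. The gain g is 0 (no titration), 0.25 (weak), 0.5 (moderate) or 1 (full). In step 2, s is 0.3–0.5 and the error in individual log CL/F has SD 0.2.

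**Step 1: the slope expected under linear PK.** Log-variance of clearance is σ² = ln(1 + 0.5²) = 0.223. True PK has no dose dependence, yet the regression slope of log CL on log dose is gσ² / (g²σ² + s²):

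- g = 0.5, s = 0.5: 0.1116 / (0.0558 + 0.25) = 0.36
- g = 0.5, s = 0.3: 0.1116 / (0.0558 + 0.09) = 0.77

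**Step 2: how often it is selected (one profile per woman, n = 40, PK strictly linear).**

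| Titration | False dose effect at p<0.001 |
|---|---|
| none, g = 0 | about 0.1% |
| weak, g = 0.25 | 3–12% |
| moderate, g = 0.5 | 18–73% |
| full, g = 1 | 86–100% |

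**Step 3: effect on predicted exposure.** If the model has CL proportional to dose^b, raising dose by a factor k multiplies AUC by k^(1−b). With k = 1.5 the true rise is 50%. Simulated slopes for g = 0.5 to 1 run from 0.39 to 0.77, giving 1.5^0.61 − 1 = 28% down to 1.5^0.23 − 1 = 10%.

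**Step 4: effect on the pregnancy and genotype terms.** This used 40 women × 3 visits and 300 runs per row, with a random-intercept model on log CL/F standing in for NONMEM. Further assumptions: early-pregnancy clearance halfway, 15% AUC error, 70% of clearance variance between women, 30% genotype carriers with 1.5-fold clearance. Dose was either re-titrated at every visit or set once per woman. Kept means dose survives both selection steps; the ratios come from models that include dose.

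| g, s | Re-titrated: dose kept | Pregnancy ratio (true 2.05) | Genotype ratio (true 1.50) | Set once: dose kept | Pregnancy ratio | Genotype ratio |
|---|---|---|---|---|---|---|
| 0, 0.4 | 0% | 2.04 | 1.51 | 0% | 2.05 | 1.49 |
| 0.25, 0.4 | 32% | 1.93 | 1.43 | 9% | 2.03 | 1.47 |
| 0.5, 0.5 | 81% | 1.84 | 1.41 | 36% | 2.04 | 1.40 |
| 0.5, 0.3 | 100% | 1.58 | 1.29 | 88% | 2.04 | 1.31 |
| 1, 0.4 | 100% | 1.44 | 1.25 | 97% | 2.06 | 1.28 |
| 1, 0.2 | 100% | 1.20 | 1.13 | 100% | 2.04 | 1.22 |

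With dose off the list, every scenario recovers 2.03–2.06 and 1.48–1.52. The pregnancy term is still selected in 97–100% of runs with dose available, except 25% in the last row under re-titration. Genotype is selected in 21–30% of runs without dose on the list, and in 4–28% with dose on it when there is any titration.

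**The case against.** A reader might infer that the search will find a dose effect and that this will hide the pregnancy effect. The documents support neither.

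- **Titration strength is unknown.** No dose distribution or dose–clearance correlation is given. Section B says half of the COW items are subjective and open to manipulation, and Section C allows that some craving is psychological. Both point to noisy titration. This stands: the selection rates show what can happen and are not forecasts.
- **Dose and its parameter are undefined.** Women take two to five doses a day, so titration may work through frequency. If frequency is assumed to rise with daily dose and the covariate is dose per administration, false selection at p<0.001 falls to about 3–4% at g = 0.5 and 31–45% at g = 1. This stands too, and is itself a reason to define the term.
- **Pregnancy is attenuated only under re-titration.** Section A contemplates women kept postpartum on their pregnancy doses; in that case the ratio stays near 2.05.
- **Aim 1 is largely insulated.** The primary dose-adjusted AUC comparison and the paired non-compartmental CL/F comparison do not use this search.
- **Genotype detection is weak anyway.** Removing dose restores an unbiased ratio but not useful power.
- **Checking dose-linearity is legitimate.** Dose-adjusted AUC relies on proportionality, and with a linear structural model the dose term is the only visible check. Agreed, but that argues for a separate check, not for automatic entry into the final model.

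**Conclusion.** The concern holds within limits. By the protocol's own account dose is set in response to symptoms and may partly reflect elimination, so a stepwise dose term cannot distinguish dose changing PK from PK changing dose. Over the assumed range of titration, false selection at p<0.001 runs from about 0.1% to 100%, and only the no-titration end is reassuring. Once in the model at moderate to full titration, the term turns a true 50% rise in AUC into a predicted 10–28%. In the three-visit simulations with any titration it pulls a 1.5-fold genotype effect to 1.13–1.47. The pregnancy ratio falls (to 1.93–1.20 over the range tried) only if dose is re-titrated between visits.

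The direction of bias is secure; its size rests on assumed titration strength, daily dose as the covariate, and clearance as the parameter tested. The damage is confined to the secondary population PK model, mainly Aim 2. The change is cheap and worth making before the model is built.

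**What to change.** In D.5.xiii, Secondary Hypotheses:

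1. Remove buprenorphine dose from the stepwise candidates, and tablet size where it only stands in for dose. Keep dose as the model input.
2. Examine dose-proportionality in one separate sensitivity run. Define dose (daily or per administration) and the parameter tested, use within-woman dose changes where available, and report the final model with and without the term.
3. State that a dose association under symptom titration is not by itself evidence of non-linear PK, and that a model containing the term will not be used for pregnancy, SNP or exposure predictions.

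The cost is one sentence in the analysis plan and one extra run, with no change to data collection or care. The downside is that a genuine dose-dependence of sublingual absorption would show only in the sensitivity run, where it remains partly confounded by titration.
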